## 4.4 Households and bed net distribution

LLINs to be evaluated will be distributed to all households included in the sample size in the areas. The total number of households required for the bio-efficacy and wash resistance study will be of equal number of samples of each type of nets. Each net type will be coded and randomly deployed to each study village and the number of nets required for the study will be calculated based on the outcome variables. Each household will be given a code relative to the code on the LLINs. This protocol can be used to monitor the durability of a LLINs product distributed in a country or for comparing several LLINs products. Users of the protocol encouraged to include one or more other LLINs for comparison, in order to provide information for future procurement. When a LLINs product is available in another denier and hence might be expected to have a different durability, it could be included for comparison.

### 4.5 Attrition

Attrition is the proportion of nets no longer in use as intended after a defined period after their distribution to the households. Attrition can be categorized by the main reasons why a net is no longer used, namely decay (e.g. Destroyed, so torn and worn out that it is considered useless for protection against mosquitoes), absence (e.g. Stolen, given away, moved) or used for other purposes.

## 4.6 Survivorship

Survivorship is the proportion of distributed nets still available for use as intended in the households to which they were given over a defined period, e.g. One year, two, three or more years.

# 4.7 Physical or fabric integrity

Reflects the number, location and size of holes in each net. When possible, the assessment can also be categorized by type of hole (burn, tear, seam failure, nibbled or chewed by animals). The physical or fabric integrity of the surviving nets can be assessed as a function of length of use, until deterioration leads to the net being discarded or used for another purpose.

# 4.8 Insecticidal activity (bio-efficacy)

Bio-efficacy is the degree of Knock Down (KD), mortality or inhibition of blood-feeding induced in susceptible mosquitoes, as determined by standard WHO test procedures and criteria (i.e. Cone bioassay, tunnel test). Insecticidal activity is associated with the type and content or availability of insecticide. The insecticide content is expressed as g/kg or mg/m² of the LLINs and is determined by the method outlined in WHO specifications for LLINs. This information is of value in interpreting data on bio-efficacy. Insecticidal activity can be assessed as a function of length of use. The interaction between insecticide type and content and the location, size and number of holes in ensuring personal protection has not been studied and remains a priority for research.

# 4.9 Evaluation of the efficacy of LLINs will be conducted in three cases:

The protocol more focuses on field studies to determine the fabric integrity, efficacy and operational acceptability of a LLINs, as summarized below. Although some observations on the safety of such nets will be carried out in the field, a preliminary safety assessment has to be undertaken, following the generic risk assessment model developed by WHO for this purpose, before any field study can be done. In addition, the physical properties of the fabric and factors relating to its structural integrity should conform to WHO specifications for netting materials.

## 4.9.1 Preliminary test

- Regeneration of insecticide and wash resistance
- Efficacy

#### 4.9.2 Small-scale field trials

- Wash resistance
- Efficacy
- Fabric integrity
- Safety observations

## 4.9.3 Large-scale field trials

- •Wash resistance
- Efficacy
- Fabric integrity
- Safety observations

# 5. LLINs study Procedure

## 5.1 Baseline Study

Feasibility study of the sites and collection of baseline information on the communities will be conducted in advance of the study. In line with this, a baseline bioassay and the chemical analysis using the procedure outlined below will be performed. In order to determine the time period required for regeneration of a LLINs after standard washing and holding at 30 °C, bioassays are carried out at 24-hour intervals on net samples washed and dried once and three times consecutively until initial biological activity is restored; nets washed three times are expected to deplete surface insecticide on the net, whereas nets washed once may not. Insecticide bioavailability (efficacy) curves will be established and compared to nets washed once and three times consecutively. The time required (in days) to reach the plateau is the period required for regeneration of the net. If the two curves are different, the longer period will be adopted as the washing interval in Phase I and Phase II studies to ensure that wash resistance is not overestimated.

Besides, the resistance of a LLINs to washing will be determined through standard bioassays carried out on nets washed at intervals required for regeneration (as determined above), using the standard WHO wash, and dried and held at 30 °C. Bioassays will be done after 0, 1, 5, 10, 15 and 20 washes or more as necessary. Each bioassay should be done just before the next wash. Regression curves should be drawn using respectively, percentage mortality and KD versus number of washes. The number of washes providing mortality and or KD above the cutoff point (more than 80% mortality after 24 hours and or above 95% KD after 60 minutes post-exposure) is reported. If a LLINs falls below the cutoff point, the study should continue until 20 washes are reached; a tunnel test (Annex 2) should then be conducted. If a WHO certificate of wash resistance or and regeneration time is provided, this procedure will be exempted.

Net samples (25 cm x 25 cm) will be individually introduced into one litter beakers containing 0.5 litters deionized water, with two grams per litter soap at PH 10–11) added just before and fully dissolved. Beakers will be immediately introduced into a water bath at 30 °C and shaken for 10 minutes at 55 movements per minute. The samples are then removed and rinsed twice for 10 minutes in clean, deionized water in the same shaking conditions as stated above. Nets dry at room temperature and stored at 30 °C in the dark between washes in a horizontal position.

#### 5.1.1 CASE I

Nets will be distributed to each household of the study villages and efficacy will be determined at the start of the project and once every two months for a total of 12 months by a trained person with close supervision of the researchers. Households will be instructed not to wash their nets as this will be done for them during each bimonthly visit by the investigators and by the peasants. During each visit, a precise history of the bed net use, including type of bed, age and number of occupants, reported usage i.e. Daily, occasionally etc., Whether the net hangs or is tucked under the bed covering and whether during the day it hangs, is rolled up or is taken down will be noted with the use of the questionnaire outlined in Annex 1. In addition, during each household visit, each net will be subject to a physical inspection, washing and a bioassay tests as outlined below.

### 5.1.2 CASE II

Side by side in the selected villages the efficacy, longevity, fabric integrity as well as the community acceptance of the LLINs will be studied every six months in the household randomized trials lasting for three years.

# 5.2 Physical condition of the nets

Each net will be subjected to a physical inspection, which will include counting the number of holes graded in three size categories; Large, by measuring them by Meter, and noting the location of the holes according to horizontal quarter sections of the sides i.e. Lower quarter, lower middle, upper middle, upper quarter or top (as outlined in Annex 2). However, if nets become so deteriorated and offered no protection they will be replaced with new ones during the course of the study.

# 5.3 Net washing

Before the start of the field study, local washing conditions will be assessed and areas where washing is deemed excessively harsh will not be eligible for inclusion. The frequency and method of washing under field conditions will also be carefully monitored during the study. If washing conditions prove excessively harsh during the trial the result will be weighed accordingly.

Nets will be washed by trained persons using a standard procedure each time following the standard WHO procedure. The nets will be washed in clean well water with a small quantity of local soap (Soap commonly available in the community; no more than two grams per litre of water). The nets will not be left in the water to soak for longer than 10 minutes and agitated gently for no more than 5 minutes by hand, and the samples should be removed and rinsed twice for 10 minutes in clean water in the same shaking condition as stated above then dried horizontally in the shade. The PH of the water will be recorded. At the same time the Participant will wash their LLINs according to the method of washing following standard WHO procedure on the basis of washing schedule shown in Table 1.

Table 1. Washing schedule

Number of washes	Months of use
Baseline	0
1 wash	2
2washes	4
3washes	6
4washes	8
5washes	10
6washes	12

### 5.3.1 In case I

Each net will be tested for wash resistance and bio-efficacy once every two months for a total of 12 months (this is case I). The bimonthly washing and bio-efficacy will be conducted in two groups:

- a) Washing to be conducted by trained persons using the standard procedure with close supervision,
- b) Washing to be conducted by the users themselves by instructing them with the method of washing.

Each net will be washed using the protocol described above, according to the schedule outlined in Table 1. Standard WHO cone bioassay will be performed on 30 randomly selected nets of each type at the start of the project and every two months for bioassay, wash resistance and physical inspection. The bioassay will be performed according to the established regeneration time for each net type thereafter cones will be placed in sub sampling locations on each net as shown in Annex 2.

Five susceptible, non-blood fed, two to five day old female susceptible *Anopheles arebiensis* mosquitoes exposed to the net for three minutes, after which they are held for 24 hours with access to the sugar solution. At least 50 mosquitoes on each net (10 replicates) and samples from different type of nets will be tested.

The results will be reported for each net tested along with the pooled results (5 x  $10 \times 4 = 200$  mosquitoes). The number of mosquitoes KD will be counted 60 minutes after exposure, and mortality (functional and effective) after 24 hours of recovery period will be recorded. An average mortality and KD value for each treatment group will then be calculated based on the number of nets for each group (WHO, 2013.1). Bioassay data for each of the sub-sampling locations on the net will also be analysed separately to see if there is a specific trend which may be indicative of more insecticide loss in lower parts of the net due to physical abrasion or lower and central parts of the net due to physical handling. Mosquitoes exposed to untreated nets will be used as controls. If mortality for a given day is between 5% and 20% on the control net it is corrected by an Abbot's formula, if mortality for a given day is > 20% all bioassays carried out on that day will be repeated. The same mosquito strain will be used throughout the study.

The bioassay tests will be carried out at a temperature of 25± 2°C and 70 ± 10% Relative Humidity (RH). If at least 80% of nets meet the cut-offs criteria for WHO cone bioassay test, then the product meets the definition for a LLINs. If a LLINs falls below the cut-off point of cone bioassays, particularly for repellent LLINs six nets with the lowest mortality or knockdown will be exposed in a tunnel test. If at least 80% fail to meet the WHO criteria for the tunnel test, then the net does not meet WHO criteria as a LLINs. The bio-cone test result using LLINs washed by trained persons using the WHO standard procedure will be used for evaluation purpose.

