#### 5.3.2 For case II

The same *Anopheline* species and same procedure implemented in all cases regarding cone bioassay, following the regeneration of the insecticide or bioavailability given by the manufacturer. The bioassay will be carried on randomly selected 30 sample nets from each type every six months. At the end of three years, at least 80% of nets meet the cut off criteria for either the WHO cone bioassay test or the tunnel test, and then the product meets the definition for a LLINs.

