## 5.4 Tunnel tests

Tunnel test done for insecticides that have a high excito-repellent effect, such as permethrin and etofenprox. Therefore, the efficacy or mortality and blood feeding inhibition of LLINs that no longer meet the criteria of standard cone bioassays will be studied in the laboratory, by releasing non-blood fed female *Anopheline arebiansis* mosquitoes, aged 5 - 8 days, in a tunnel (square section 25cm x 25cm) made of glass, 60 cm length. At each end of the tunnel, a 25cm square cage is fitted with extension and covered with polyester netting.

At one third of the length, a disposable cardboard frame is placed in the treated netting sample. The surface of netting "available" to mosquitoes is 400 cm^2 (20cm x 20cm), with nine holes each one cm in diameter, one hole is located at the centre of the square; the other eight are equidistant and located at five cm from the border. In the short section of the tunnel, a bait unable to move is placed in the cage at the end of the long section of the tunnel, 100 females are introduced at 18:00. Females *An. arebiansis* will be released to fly in the tunnel, but have to make contact with the piece of netting and locate the holes in it before passing through to reach the bait.

The following morning, at 09:00, the mosquitoes are removed and counted separately from each section of the tunnel and the immediate mortality is recorded. Live females are placed in plastic cups with honey solution; delayed mortality is recorded after 24 hours. During tests, cages are maintained at  $27^{\circ}$ C  $\pm 2^{\circ}$ C and  $80\%\pm 10\%$  RH under subdued light. Several tunnels will be used simultaneously, one tunnel with untreated netting always being used as a negative control. Blood-feeding inhibition is assessed by comparing the proportion of blood-fed females alive or dead in treated and control tunnels. Overall mortality is measured by pooling the immediate and delayed (24hour) mortalities of mosquitoes from the two sections of the tunnel (Annex 2).

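### The tunnel-test rules for Case I and Case II use different nets and different denominators for the same LLIN decision, so the same net results can be rejected under one and accepted under the other

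*Protocol*

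**What the plan says.** Three sections of the Protocol govern the step from cone test to tunnel test.

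- **Section 5.3.1, Case I (12 months).** "Standard WHO cone bioassay will be performed on 30 randomly selected nets of each type". The first criterion is: "If at least 80% of nets meet the cut-offs criteria for WHO cone bioassay test, then the product meets the definition for a LLINs". If the product falls short, "six nets with the lowest mortality or knockdown will be exposed in a tunnel test", and then: "If at least 80% fail to meet the WHO criteria for the tunnel test, then the net does not meet WHO criteria". The sentence speaks of a net, but an 80% rule can only describe a product. The section adds that only results from nets washed by trained persons are used for evaluation.
- **Section 5.3.2, Case II (three years).** "The bioassay will be carried on randomly selected 30 sample nets from each type every six months". At the end of three years the product qualifies if "at least 80% of nets meet the cut off criteria for either the WHO cone bioassay test or the tunnel test". What is carried over from Case I is the "same procedure implemented in all cases regarding cone bioassay". How nets are chosen for the tunnel is not mentioned.
- **Section 5.4, tunnel tests.** "LLINs that no longer meet the criteria of standard cone bioassays will be studied in the laboratory". No maximum number of nets is given.

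**The concern.** Both cases settle the same product status, and section 3.1 says the results serve registration and procurement. The rules that settle it differ in three ways:

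- **Which nets are tunnel-tested.** Case I takes the six worst on the cone test. Case II and section 5.4 give no such limit.
- **What the 80% is a percentage of.** In Case I it appears to be the six tunnelled nets, so cone passes drop out of the verdict. In Case II it is all sampled nets.
- **What the 80% counts.** Case I rejects when 80% fail. Case II accepts when 80% meet the criteria. Case I does not say what follows when fewer than 80% fail.

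A product can therefore pass or fail according to which section is applied. The most exposed products are the excito-repellent ones, for which section 5.4 says the tunnel test exists. If the conflict is resolved only once results are known, the choice of rule could decide the verdict.

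**Working it through.** The Protocol gives no calculated figure for these rules, so there is none to reproduce. The check turns the percentages into counts and applies both rules to the same results.

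**Inputs.** 30 nets per product (5.3.1 and 5.3.2); 80% threshold (both); six nets in the Case I tunnel step (5.3.1). The Case I tunnel step is taken to start when the product misses the 80% cone criterion.

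**Step 1: thresholds.** 0.80 × 30 = 24, so cone acceptance needs 24 passes and the tunnel step starts only with 23 or fewer, that is, at least 30 − 23 = 7 cone failures. 0.80 × 6 = 4.8, so Case I rejection needs at least 5 of 6 tunnel failures.

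**Step 2: the Case I denominator.** If the 80% referred to 30 nets, rejection would need 24 tunnel failures from six tested nets, which is impossible. Six is the only reading under which the rule can operate.

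**Step 3: nets without a tunnel result.** With at least 7 cone failures and six tunnel tests, between 7 − 6 = 1 and 30 − 6 = 24 cone-failing nets have no tunnel result. The Case I tunnel verdict is the same function of six results whether 7 or 30 nets failed the cone test.

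**Step 4: the same results under both rules.**

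| Cone passes | Tunnel results | Case I | Case II |
|---|---|---|---|
| 23 | 1 of the six worst passes | 5/6 = 83% fail: rejected | (23 + 1)/30 = 80%: meets |
| 10 | six worst all fail, other 14 all pass | 6/6 = 100% fail: rejected | (10 + 14)/30 = 80%: meets |
| 10 | 2 of the six worst pass, others not tunnelled | 4/6 = 67% fail: not rejected | (10 + 2)/30 = 40%: does not meet |

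The first row needs no assumption about the seventh cone-failing net: if it were tunnelled and passed, Case II would give 25/30, still a pass. The third row treats nets without a tunnel result as not meeting the criteria. If the other 14 were tunnelled, Case II would need 24 − 12 = 12 of them to pass.

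**Step 5: how often the rules differ.** These are counts of possible outcomes, not probabilities.

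- Only six nets tunnelled: 24 values of cone passes (0–23) × 7 values of tunnel passes (0–6) = 168 outcomes. The rules agree in 67. In 1 Case I rejects and Case II accepts (first row of the table). In 100 Case I does not reject and Case II is not met.
- All cone-failing nets tunnelled for Case II: of 2,268 outcomes, 72 are rejected by Case I and accepted by Case II, and 1,055 are not rejected by Case I and not met in Case II.

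**The case against.** **The cases are different studies.** Case I is a 12-month study with scheduled washing and Case II a three-year household trial, so no single dataset is planned to be scored under both rules. That is so, but both rules decide the same LLIN status. A different readout time does not explain a different denominator or a different direction of the 80% rule.

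**The tunnel branch is conditional.** It arises only after cone failure and mainly for repellent products. This limits how often the conflict arises, but those are the products the branch was written for.

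**Stronger readings that the text does not support.** A reader might infer any of the following:

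- *That identical data always give opposite verdicts.* They can. With six nets tunnelled the rules agree in 67 of 168 outcomes, and only one outcome is a stated rejection against a stated acceptance. The 100 others treat not rejected as accepted, which section 5.3.1 never says.
- *That cone-failing nets beyond six have no score.* They have a failing cone result and lack only a tunnel result.
- *That Case II is capped at six tunnel tests, so 13 or more cone failures make acceptance impossible* (at most 17 + 6 = 23 of 30). Section 5.3.2 carries over the cone procedure only, and section 5.4 has no cap.
- *That Case I is far stricter than Case II.* With 7 cone failures and an assumed, independent 50% tunnel pass rate, Case II accepts with probability 1 − 0.5⁷ = 99%. If the Case I sentence were reversed to require 5 of 6 passes, Case I would accept with probability 7/64 = 11%. That rule is not in the Protocol. As written, Case I rejects with probability 7/64 and so does not reject in 57/64 = 89%. The size and sign of any such gap depend on the direction of the 80% rule and on the assumed pass rate.

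**Conclusion.** The concern holds as an inconsistency between sections 5.3.1, 5.3.2 and 5.4. Following the Case I rule as written can produce a verdict that contradicts the Protocol's own Case II criterion. The case of 23 cone passes with 1 of 6 tunnel passes shows this by counting alone. It assumes only that the Case I tunnel 80% refers to the six tunnelled nets and that the rule is a product-level one.

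The opposite conflict, where Case I lets through a product that Case II would not, is weaker. It requires reading not rejected as accepted and, in the example of 10 cone passes, also that only six nets are tunnelled. The missing acceptance rule in Case I is itself part of the defect.

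No probability of conflict can be given from the Protocol, because it states no expected cone or tunnel pass rates. The sections should be reconciled before any product is scored.

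**What to change.** State one rule and refer to it from sections 5.3.1, 5.3.2 and 5.4. The Protocol's own Case II rule is a natural candidate:

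- The denominator is all sampled nets used for evaluation. In Case I these are the nets washed by trained persons. Section 5.3.1 should say whether the 30 nets per type are all in that group. If 30 are evaluated, the threshold is 24.
- A net counts if it passes the cone test or, having failed it, passes the tunnel test.
- The product meets the definition if at least 80% of nets count, and otherwise does not. This replaces the separate 80%-fail sentence and fills the gap left by it.
- The selection of six nets is removed. Cone-failing nets are tunnel-tested until 80% is reached or can no longer be reached. With 30 nets and *f* cone failures, testing stops at *f* − 6 tunnel passes (accept) or at 7 tunnel failures (not met, since 30 − 7 = 23). Stopping this way cannot change the verdict that testing all of them would give.

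The text change is small. The practical cost is laboratory work. A product with 7 cone failures may need a single tunnel test, but one with many failures may need well over six, at most one per cone-failing net and so up to 30. Each is an overnight run with 100 mosquitoes (section 5.4), although several tunnels can run at once. If the investigators wish to keep a six-net tunnel step for feasibility, the Protocol should apply it to both cases, state its denominator, and say how nets without a tunnel result are counted.

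### The Case I tunnel rule puts the 80% on failing nets, while the Case I cone rule and the Case II rule put it on passing nets; most tunnel results are left without a verdict

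*Protocol*

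**What the plan says.** Three decision rules in the protocol carry an 80% threshold.

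- **Case I, cone (section 5.3.1).** "If at least 80% of nets meet the cut-offs criteria for WHO cone bioassay test, then the product meets the definition for a LLINs". The sample is given in the same section: "Standard WHO cone bioassay will be performed on 30 randomly selected nets of each type".
- **Case I, tunnel (section 5.3.1, same paragraph as the cone rule).** If the product falls below the cone cut-off, "six nets with the lowest mortality or knockdown will be exposed in a tunnel test". Then: "If at least 80% fail to meet the WHO criteria for the tunnel test, then the net does not meet WHO criteria".
- **Case II (section 5.3.2).** After three years, with 30 nets of each type sampled, the product meets the definition if "at least 80% of nets meet the cut off criteria for either the WHO cone bioassay test or the tunnel test".

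Section 5.4 describes the tunnel method. It says that nets no longer meeting the cone criteria will be studied this way, but gives no number of nets and no product-level decision rule.

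**The concern.** In two of the three rules the 80% is a share of nets that pass. In the Case I tunnel rule it is a share of nets that fail. Turning the threshold round does not give the complement of a pass rule: the opposite of at least 80% passing is more than 20% failing, not at least 80% failing. The gap between the two covers most of the possible results on six nets.

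The Case I sentence also gives only a condition for rejection. It does not say what follows when fewer than 80% fail, and it does not say whether the 80% refers to the six tunnel-tested nets or to all 30 sampled nets.

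The sentence decides whether a product counts as long-lasting, and section 3.1 ties the protocol to product registration and national procurement. No other Case I tunnel rule in the protocol corrects it.

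**Working it through.** **Inputs.** 30 nets per type in the cone test (5.3.1, and the same number in 5.3.2); six nets in the Case I tunnel test (5.3.1); 80% threshold in all three rules. The protocol gives no error rate or operating characteristic for the tunnel rule, so there is no stated figure to reproduce.

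**Step 1: the rule as written, on six nets.** 0.80 × 6 = 4.8, so rejection needs at least 5 failures.

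| Tunnel passes of 6 | Failures | Share failing | Rejected as written? |
|---|---|---|---|
| 0 | 6 | 100% | yes |
| 1 | 5 | 83.3% | yes |
| 2 | 4 | 66.7% | no, verdict not stated |
| 3 | 3 | 50.0% | no, verdict not stated |
| 4 | 2 | 33.3% | no, verdict not stated |
| 5 | 1 | 16.7% | no, verdict not stated |
| 6 | 0 | 0% | no, verdict not stated |

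Five of the seven possible results, including six passes out of six, have no stated outcome.

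**Step 2: the other denominator.** If the 80% meant all 30 nets, rejection would need 0.80 × 30 = 24 tunnel failures. Six tunnel-tested nets cannot supply 24, so the rule could never operate on tunnel results. The six nets are the only workable reading, but the text does not say so.

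**Step 3: comparison with the Case II criterion on the same nets.** Let k be the number of cone passes among 30 and t the number of tunnel passes among the six. Assume that all six tunnel-tested nets failed the cone test. At least seven nets fail whenever k is 23 or less, so there are enough of them. The Case II criterion then needs k + t ≥ 24, that is t ≥ 24 − k. The Case I sentence rejects when t ≤ 1.

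| Cone passes k | Tunnel passes needed (24 − k) | Tunnel results on which the two differ |
|---|---|---|
| 23 | 1 | t = 1: rejected although 24/30 |
| 22 | 2 | none |
| 21 | 3 | t = 2: not rejected at 23/30 |
| 20 | 4 | t = 2 or 3 |
| 19 | 5 | t = 2 to 4 |
| 18 | 6 | t = 2 to 5 |
| 17 or fewer | 7 or more, unattainable | t = 2 to 6 |

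**Step 4: one example in each direction.**
- k = 10, t = 2: 4/6 = 66.7% fail, so no rejection. Combined passes are 10 + 2 = 12, and 12/30 = 40%, well short of 24.
- k = 23, t = 1: 5/6 = 83.3% fail, so rejected. Combined passes are 23 + 1 = 24, and 24/30 = 80%, which meets the criterion.

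The rejection line in Case I matches the Case II criterion for every tunnel result only at k = 22.

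**The case against.** The strongest reply is that this is a visible slip of wording, and that less follows from it than might appear. Several parts of that reply stand.

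- **Not rejected is not accepted.** The text says what happens if at least 80% fail; it does not say that this is the only route to rejection. The only acceptance rule stated for Case I is the cone rule. A reader might infer that the protocol lets ineffective nets through. The documents do not support that: they leave the outcome open.
- **No 5-of-6 rule is stated.** A reader might suppose that at least five of the six tunnel nets were meant to pass, and compare probabilities under that rule. It appears nowhere. It would also clash with Case II: 22 cone passes plus 2 tunnel passes reach 24 of 30, yet fail 5 of 6. Because the six nets are chosen as the worst on the cone test, their pass rate is not the product's, and 2 of 6 among them can be compatible with 80% overall.
- **The six-net limit is stated for Case I only.** Section 5.3.2 carries over the procedure for the cone bioassay and sets no tunnel number. If all 20 cone-failing nets in the first example were tunnel-tested, the product could still reach 24 of 30. The example compares two criteria on one data set with six tunnel nets; it does not forecast a Case II result.
- **The cases cover different periods.** Case I runs 12 months and Case II three years, and section 2 defines a long-lasting net partly by three years of field use. This lowers the stakes of the Case I verdict. It does not remove them, because section 5.3.1 issues its verdict in the same terms.

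None of this makes the sentence workable: its direction still conflicts with the two neighbouring rules, its denominator is unnamed, and most results have no verdict.

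**Conclusion.** The point holds. The Case I tunnel sentence is wrong as written: it sets the 80% on failing nets where the Case I cone rule and the Case II rule set it on nets that meet the criteria. On six nets it rejects at 5 or 6 failures and gives no verdict for 2 to 6 passes. Against the Case II criterion on the same 30 nets it errs in both directions: no rejection at 12 of 30 (40%), rejection at 24 of 30 (80%).

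This rests on three assumptions: the 80% refers to the six tunnel-tested nets; the word net in that sentence means the product; and, for the comparison, the Case II criterion is applied with six tunnel nets, all of which failed the cone test. It does not show that poor products would be accepted, nor how often a wrong verdict would occur. It should be corrected before any Case I verdict is issued.

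**What to change.** Replace the Case I tunnel sentence in section 5.3.1 with the criterion already in section 5.3.2, stated in full: each of the 30 sampled nets is scored as passing if it meets the cone or the tunnel criteria; the product meets the definition if at least 80% of the sampled nets (24 of 30) pass, and otherwise it does not. Name the denominator as all sampled nets. Do not add a separate threshold on the six tunnel nets, since that would bring back a conflict between rules.

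State for both cases how many cone-failing nets go to the tunnel. Section 5.3.1 says six; sections 5.3.2 and 5.4 give no number.

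**Cost.** The change is to wording. If six nets are kept, Case I needs no extra laboratory work, but the tunnel can add at most six passes. A product with fewer than 24 − 6 = 18 cone passes then cannot qualify, however well its other nets might do in the tunnel, and the protocol should say so. Testing more cone-failing nets would remove that ceiling at the price of more tunnel tests.
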